## 2. Study Objectives and Endpoints

### 2.1. Study Objectives

#### 2.1.1. Primary Objective

The primary objective is to assess the efficacy of DCR-PHXC in reducing urinary oxalate burden in patients with PH (types 1 and 2).

#### 2.1.2. Key Secondary Objective

The key secondary objective is to identify the proportion of participants with normalized or near-normalized urinary oxalate excretion (Uox).

### **2.1.3. Secondary Objectives**

The secondary objectives are:

1. To evaluate the effect of DCR-PHXC on stone burden in patients with PH.
2. To evaluate the effect of DCR-PHXC on plasma oxalate in patients with PH.
3. To evaluate the effect of DCR-PHXC on eGFR.
4. To assess the safety of DCR-PHXC in patients with PH.
5. To characterize the pharmacokinetics (PK) of DCR-PHXC in patients with PH.

### **2.1.4. Tertiary/Exploratory Objectives**

The tertiary/exploratory objectives are:

1. To evaluate the effect of DCR-PHXC on stone events in patients with PH.
2. To assess the efficacy of DCR-PHXC in reducing Uox burden over 6 months period in patients with PH.
3. To assess the efficacy of DCR-PHXC in reducing Uox burden at month 6 in patients with PH.
4. To evaluate the effect of DCR-PHXC on urinary oxalate-to-creatinine ratio in patients with PH.
5. To evaluate the effect of DCR-PHXC on quality of life (QoL) assessments in patients with PH.
6. To evaluate the relationship between Uox spot urine and 24-hour urine measurement in patients with PH.

## **2.2. Study Endpoints**

### **2.2.1. Safety Endpoints**

The safety endpoints of this study include the following:

- Adverse events (AEs), serious AEs (SAEs) and AEs of special interest (AESI)
- Change from baseline in 12-lead ECG
- Physical examination findings
- Vital signs
- Clinical laboratory tests

## 2.2.2. Efficacy Endpoints

### 2.2.2.1. Primary Efficacy Endpoint

The primary efficacy endpoint of this study is the area under the curve from Day 90 to Day 180 ( $AUC_{24\text{-hour } U_{ox}}$ ), based on percent change from baseline in 24-hour  $U_{ox}$  (adjusted per  $1.73 \text{ m}^2$  body surface area [BSA] in participants aged  $<18$  years). Further details of calculations are provided in Section 6.1.9.

### 2.2.2.2. Key Secondary Endpoint

The key secondary endpoint is the proportion of participants with a 24-hour  $U_{ox}$  level  $<0.46$  mmol/24 hours (normalized), or  $\geq 0.46$  to  $<0.6$  mmol/24 hours (near-normalized) (adjusted per  $1.73 \text{ m}^2$  body surface area [BSA] in participants aged  $<18$  years) on at least two consecutive visits, beginning with Day 90. Further details of calculations are provided in Section 6.1.9.

### 2.2.2.3. Secondary Efficacy Endpoints

The secondary efficacy endpoints of this study include the following:

- Percentage change in the summed surface area and number of kidney stones identified via kidney ultrasound from baseline to Day 180
- Percentage change in plasma oxalate from baseline to Day 180 (for adults only)
- Rate of change in eGFR from baseline to Day 180.
- Population and individual PK parameters for DCR-PHXC

[figure not shown]
### 2.2.2.4. Tertiary/Exploratory Efficacy Endpoints

The tertiary/exploratory efficacy endpoints include the following:

- Number of stone events over a 6-month period
- $AUC_{24\text{-hour } U_{ox}}$  from Day 1 to Day 180, based on percent change from baseline
- Percentage change in 24-hour  $U_{ox}$  from baseline to Day 180
- AUC of 24-hour urinary oxalate-to-creatinine ratio ( $AUC_{24\text{-hour } U_{ox}:\text{creatinine}}$ ) from Day 90 to Day 180, based on percent change from baseline
- Change from baseline to Day 180 in the Short Form (36) Health Survey (SF-36) and EQ-5D-5L in adults; and in the PedsQL™ in children (including adolescents)
- $U_{ox}$  in spot urine and 24-hour urine

## 2.2.3. Pharmacokinetic Variables

Pharmacokinetic parameters to be analyzed will be described in detail in a separate Pharmacokinetic Analysis Plan (PKAP). PK TLF generation and validation will be covered in a separate analysis plan.

### 3. Overall Study Design and Plan

#### 3.1. Overall Design

This is a 6 month, randomized, placebo-controlled, double-blind study of DCR-PHXC in patients with primary hyperoxaluria (PH1 and PH2).

#### 3.2. Sample Size and Power

Approximately 40 participants will be screened to achieve an estimated total of 36 evaluable participants.

For the sample size calculations, the primary endpoint of  $AUC_{24\text{-hour } U_{ox}}$  from Day 90 to Day 180 based on percent change from baseline was used. The group sequential design with pre-specified alpha spending for interim analysis and final analysis was utilized. The randomization ratio is 2-to-1 (active-to-placebo). The primary hypothesis to be tested is a one-sided superiority hypothesis at the significance level of 0.025. The  $AUC_{24\text{-hour } U_{ox}}$  in the placebo arm is assumed to be 0, as the  $U_{ox}$  values may oscillate up and down from baseline due to measurement variability. The  $AUC_{24\text{-hour } U_{ox}}$  in the active arm is assumed to be 3600 based on a 40% decrease over the 90 days. The effect size is assumed to be 1.2. Under these assumptions, the sample size of 36 patients (24 in the active arm and 12 in the placebo arm) will yield a power of approximately 94%. All calculations were performed using [REDACTED].

The above sample size calculation was performed under the assumption that there may be an interim analysis to re-estimate sample size after two-thirds of participants complete the study. However due to late enrollment experienced in the study, an interim analysis will not be performed.

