9.2. SAMPLE SIZE DETERMINATION

Approximately 40 participants will be screened to achieve an estimated total of 36 evaluable participants.

For the sample size calculations, the primary endpoint of the AUC of 24-hour Uox from Day 90 to Day 180 based on percent change from Baseline is used. The group sequential design with prespecified alpha spending for interim analysis and final analysis is utilized. The randomization ratio is 2:1 (active:placebo). The primary hypothesis tested is a 1-sided superiority hypothesis at the significance level of 0.025. The AUC Uox in the placebo arm is assumed to be 0, as the Uox values may oscillate up and down from baseline due to the measurement variability. The AUC Uox in the active arm is assumed to be 3600 based on 40% decrease over the 90 days. The effect size is assumed to be 1.2. Under these assumptions, the sample size of 36 patients (24 in the active arm and 12 in the placebo arm) will yield a power of approximately 94%. All calculations were performed using [REDACTED]. There may be one interim analysis to re-estimate sample size after two-thirds of participants complete the study.

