9.5.1. Efficacy Analyses

Endpoint	Statistical Analysis Methods
Primary	The AUC of 24-hour Uox from Day 90 to Day 180, based on percent change from baseline, will be compared between the active treatment group and placebo group. A multiple imputation approach will be used to handle missing Uox data and then calculate the AUC. ANCOVA model with the Uox baseline value, age category, and eGFR category as the covariate will be used. The primary efficacy analysis will be based on MITT population. The normality will be investigated by examining Q-Q plots and histograms. In case the data are not normal, they will be log-transformed.
Key Secondary	The proportion of participants whose Uox values normalized or near-normalized on at least 2 consecutive visits starting at Day 90 will be summarized by treatment group. A 1-sided Fisher's exact test at significance level alpha of .025 will be used for comparison between treatment groups. The analysis will be performed based on MITT population.
Secondary	For percent change from baseline to Day 180 in the summed surface area and number of kidney stones, and plasma oxalate, the Wilcoxon Rank Sum test will be used. Rate of change in eGFR will be summarized by treatment group. The mixed model with the Uox baseline value and the endpoint's baseline value (eGFR) as covariates will be used.
Exploratory	The number of stone events will be analyzed using an exact Poisson regression model. The model will include treatment group and baseline stone events rate (continuous). More details will be provided in the SAP.

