9.6. INTERIM ANALYSES

An interim analysis may be conducted upon completion of two-thirds of the participants for the purpose of re-evaluation of sample size. The interim unblinded analysis will be performed by an independent statistician other than the person responsible for the primary analysis of this study and treatment codes will be revealed to that party only. The re-evaluation of sample size will use the conditional power approach based on the test statistics from the interim analysis. A minimal fraction of alpha (.0001) will be spent at the interim analysis, as the trial will not be stopped early for efficacy or futility based on the results from the interim analysis. The final analysis will use alpha of 0.0249 for the primary endpoint, in order to preserve an overall type I error at the 1-sided 0.025 level.

Conditional power will be calculated based on the observed treatment effect and standard error at the interim analysis. Conditional power will be partitioned into three zones – favorable, promising, and unfavorable.

- In the favorable zone, the interim analysis results are sufficiently favorable, and the conditional power is sufficiently high, so that the study can continue with the original sample size and an increase is not needed.
- In the promising zone, the conditional power is moderately high and can be elevated by an increase of sample size to recover the targeted power $1-\beta$ at least 80%.
- In the unfavorable zone, the conditional power is fairly low, and cannot achieve the targeted level with an increase in sample size. In this instance, the study would continue with the original planned sample size.

The SAP will describe the planned interim analyses in greater detail.

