### 4.2. Interim Analysis and Data Monitoring

No interim analysis will be conducted. The final analysis will use an alpha of 0.025.

A DSMC was convened to provide periodic review of the efficacy and safety data. The DSMC is comprised of three voting members independent of the study team and sponsor. At a minimum, the DSMC meets:

- prior to the first participant enrolled,
- after the first five participants have completed the Day 30 Visit,
- after three adolescent participants (aged 12 to 17 years) have been enrolled in the DCR PHXC arm and have completed the Day 60 Visit, and
- periodically thereafter (depending on enrollment).

Children aged 6 to 11 years were not enrolled until modelling and simulation of the PK and PD data determined an appropriate dose for that age group and the DSMC has reviewed safety data from at least the first 60 days of DCR-PHXC treatment (2 doses plus 30 days of follow up) in three adolescent participants (aged 12 to 17 years). For participants 12 to 17 years of age, the

DSMC affirmed that the overall risk-benefit balance remains positive. Moreover for this age group no AEs of severe intensity considered to be drug related (per selective unblinding by DSMC) and no SAEs suspected to be drug related (per unblinding by DSMC) were observed to have occurred.

The DSMC will review unblinded safety and efficacy data and will make determinations on whether to continue the study following each periodic review of the data. A DSMC charter containing details of the operation of the DSMC will be developed in conjunction with the members of the DSMC before the first meeting and will be modified as required. The sponsor may request additional reviews should any other findings/issues pertaining to safety or efficacy emerge requiring DSMC review.

The unblinded analyses will be performed by the [REDACTED] unblinded statistician and [REDACTED] unblinded SAS programmers. The [REDACTED] unblinded statistician is an independent statistician other than the author of this plan or the person responsible for the primary analysis of this study. Treatment codes will be revealed to those parties only.

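### The stated power of about 94% does not follow from the stated inputs, which give about 91% to 92%; the gap was already in the Protocol and is minor

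*SAP*

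**What the plan says.** SAP 3.2 lists the inputs: 2:1 allocation, placebo mean AUC of 0, active mean AUC of 3600, effect size 1.2. On the test it says "The primary hypothesis to be tested is a one-sided superiority hypothesis at the significance level of 0.025". From these it concludes that "the sample size of 36 patients (24 in the active arm and 12 in the placebo arm) will yield a power of approximately 94" per cent. The software name is redacted. No SD, test type or covariate correlation is given.

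Protocol 9.2 has the same sentence ("24 in the active arm and 12 in the placebo arm) will yield a power of approximately 94" per cent), and so does the statistical overview in Protocol 1.1.1.

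The next paragraph of SAP 3.2 adds: "The above sample size calculation was performed under the assumption that there may be an interim analysis to re-estimate sample size", and then "However due to late enrollment experienced in the study, an interim analysis will not be performed". SAP 4.2 confirms: "No interim analysis will be conducted. The final analysis will use an alpha of 0.025". Protocol 9.6 had planned to spend 0.0001 at the interim and 0.0249 at the end, with no early stopping for efficacy or futility. Its only route to extra power was a larger sample: "In the promising zone, the conditional power is moderately high and can be elevated by an increase of sample size".

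The planned primary test is an ANCOVA. Protocol 9.5.1 says "ANCOVA model with the Uox baseline value, age category, and eGFR category as the covariate will be used", and SAP 8.1 specifies the same model.

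**The concern.** SAP 3.2 presents the power as the result of the assumptions listed just before it, so a reader should be able to recover it from them. The usual calculations for 24 versus 12 at effect size 1.2 and one-sided 0.025 give a lower figure. The SAP then says that the design behind the calculation will not be run as planned, and gives no power for the fixed design that will be.

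What is at stake is the accuracy of a reported design figure. A reader would take the type II error to be about 6%, whereas the stated inputs imply 7.6% to 9.3%.

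**Working it through.** **Inputs.** From SAP 3.2: n = 24 active and 12 placebo, effect size d = 1.2, one-sided alpha 0.025. From Protocol 9.6: interim alpha 0.0001 and final alpha 0.0249; SAP 3.2 places the interim after two-thirds of participants. The SD is not stated; 3600/1.2 implies 3000.

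**Noncentrality.** 1.2 × sqrt(24 × 12/36) = 1.2 × sqrt(8) = 3.394.

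**Attempt to reproduce 94% from the stated inputs**

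| Method | Formula | Power | Below 94% by |
|---|---|---|---|
| Normal approximation | Φ(3.394 − 1.960) | 92.4% | 1.6 points |
| Two-sample t, 36 − 2 = 34 df | P(noncentral t > 2.032) | 90.9% | 3.1 points |
| ANCOVA, 30 error df, no covariate gain | P(noncentral t > 2.042) | 90.7% | 3.3 points |

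The ANCOVA error df are 36 less 1 (intercept), 1 (treatment), 2 (three age categories), 1 (eGFR category) and 1 (baseline Uox), which is 30. None of the three results rounds to 94%.

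**Does rounding of the effect size explain it?** Values that round to 1.2 run from 1.15 to just under 1.25.

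- By t-test, power over that range is about 88.5% to 93.0%, so it never reaches 94%. It would need d = 1.279.
- By normal approximation, the range is about 90.2% to 94.2%. It reaches 94% only from d = 1.243 upward.

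**Does dropping the interim explain it?**

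- Fixed design, alpha 0.025: 92.42% (normal approximation).
- Fixed design, alpha 0.0249: 92.40%.
- Two looks, 0.0001 at information fraction 2/3, overall 0.025, no sample size increase: 92.42%.

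On the t-test, moving from alpha 0.0249 to 0.025 changes power from 90.91% to 90.94%. The cancellation therefore moves power by about 0.03 points at most, and the gap was already present in Protocol 9.2 and 1.1.1.

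**What would give about 94%**

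- *Unrounded effect size with a normal approximation.* d = 1.243 gives 94.0%; d = 1.25 gives 94.2%.
- *Covariate gain in the ANCOVA.* A covariate-outcome correlation r raises the effective d to 1.2/sqrt(1 − r²). With 30 error df, r = 0 gives 90.7%, r = 0.3 gives 93.1%, r = 0.357 gives 94.0% and r = 0.4 gives 94.8%. These values of r are assumptions; the documents give none.
- *Equal allocation.* 18 versus 18 gives 93.8% by t-test, but the design is 2:1.
- *Sample size re-estimation.* Simulation with an interim at 24 of 36 gave about 93.2% to 94.9%, assuming lower promising-zone limits of 0.3 to 0.5, caps of 45 to 72 participants and conditional power targets of 80% to 90%. The zone limits and caps are assumptions, since the documents state neither. In these runs the mean sample size was about 36.6 to 40.0, above the 36 to which the stated power is tied.

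**The case against.** The strongest defence is that no arithmetic error has been shown. The figure is labelled approximate, and the effect size is printed to one decimal. The normal approximation comes within 1.6 points, and an unrounded value of 1.243 would give 94.0%. A moderate covariate gain in the planned ANCOVA would also do it. The software is redacted, and redaction is not an omission by the sponsor. SAP 3.2 also says openly that the calculation was made when an interim was still possible.

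Much of this stands. The sponsor's calculation may be right on inputs that the visible text does not show, and a reader is not misled about the status of the interim. But neither the redaction nor the disclosure supplies the missing input. A software name would not in itself give an unrounded effect size or a covariate correlation, and the sentence ties 94% to assumptions that do not yield it.

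A reader might infer that cancelling the interim made 94% out of date. The documents do not support that. With 0.0001 of alpha and no early stopping, the interim costs almost no power and its removal restores almost none. Only the sample size increase could link the two; that rests on assumed zones and caps and fits poorly with a sentence about 36 participants.

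A reader might also infer that the trial is underpowered. That does not follow either: each of the three methods gives more than 90% at effect size 1.2.

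**Conclusion.** The sentence is wrong as written, with minor consequences. At 24:12, effect size 1.2 and one-sided 0.025, power is about 91% (t-based) to 92% (normal approximation), not about 94%. The discrepancy applies equally to the Protocol and the SAP.

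This takes the effect size as exactly 1.2, all 36 participants as contributing, and no covariate gain. If the sponsor holds an unrounded effect size or assumed a covariate correlation, 94% may be defensible, but the plan should then say so.

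**What to change.** In SAP 3.2, restate the power for the final fixed design. For example: with an effect size of 1.2, one-sided alpha 0.025 and no interim analysis, 24 active and 12 placebo participants give approximately 91% power (t-based, no covariate gain assumed). If a normal approximation is preferred, name it and give approximately 92%. Keep 94% only with the unrounded effect size or the assumed covariate gain stated beside it. If an SD is quoted, label 3000 as implied by 3600/1.2, because the documents do not state one.

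If the Protocol is amended, correct only the power figure in 9.2 and 1.1.1 and leave its interim text as it is.

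The cost is one sentence in the SAP and one figure in each of two Protocol sections. The reported power may look slightly less favourable. Enrolment, the analysis and type I error do not change.

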#### 3.3. Study Population

The study population includes male and female patients, at least 6 years of age, with genotype-confirmed PH1 or PH2.

#### 3.4. Treatments Administered

Study intervention will be administered in clinic as a subcutaneous (SC) injection into the abdomen or thigh. In adults and adolescents (aged 12 to 17 years) weighing  $\geq 50$  kg, study intervention will be administered once monthly at a dose of 170 mg DCR-PHXC (or the equivalent volume of placebo). In adults and adolescents weighing  $< 50$  kg, study intervention will be administered once monthly at a dose of 136 mg DCR-PHXC (or the equivalent volume of placebo). Participants who begin the study weighing less than 50 kg will have their dose increased to the 170 mg dose should they reach the 50 kg threshold. Participants receiving the 170 mg dose will not have their dose decreased to the 136-mg dose should they fall below the 50-kg threshold.

The dose for participants aged 6 to 11 years was determined from an evolving PK/pharmacodynamic (PD) modeling and simulation (M&S) model, as detailed in Section 4.3 of the protocol. The model-derived dose of 3.5 mg/kg was approved by the data safety monitoring committee (DSMC) upon review of the appropriate safety data.

An unblinded pharmacist or designee will prepare each dose of DCR-PHXC or placebo as detailed in Section 6.2.4 of the protocol.

### 3.5. Method of Assigning Participants to Treatment Groups

Eligible participants will be randomized in a 2-to-1 (DCR-PHXC-to-placebo) ratio using an interactive web response system (IWRS).

To balance the participants between the intervention arms based on 2 factors: age (6 to 11, 12 to 17, or  $\geq 18$  years) and eGFR (eGFR  $< 45$  mL/min, eGFR  $\geq 45$  mL/min), an adaptive randomization via minimization method will be used to allocate patients to treatment groups. Minimization aims to ensure that the intervention arms are balanced with respect to the predefined factors, as well as for the number of patients in each arm. Minimization can be especially helpful for studies with small sample sizes as the minimization produces better balance than standard stratified randomization methodology. Imbalance scores are calculated for the possible patient allocations to treatment groups, which represent the imbalance that would be generated in each of the treatment arms, while taking into account these two factors. Participants will be assigned to the treatment that would generate the lowest amount of imbalance with a probability of 80%, and to the treatment that would generate the highest amount of imbalance with a probability of 20%. Please refer to the study adaptive randomization plan for further details on the minimization algorithm used for treatment assignment.

At the beginning of the study, only two age groups were enrolled (12 to 17 and  $\geq 18$ ). Children aged 6 to 11 years were not enrolled until modeling and simulation of PK and PD data determined an appropriate dose for that age group and the DSMC reviewed safety data from at least the first 60 days of DCR-PHXC treatment (two doses plus 30 days of follow up) in three adolescent participants (aged 12 to 17 years). Concerning participants 12 to 17 years of age, the DSMC affirmed that the overall risk-benefit balance remains positive, and that no AEs of severe intensity considered to be drug-related (per selective unblinding by DSMC), and no SAEs suspected to be drug-related (per unblinding by DSMC) have occurred in participants 12 to 17 years of age. This will not affect the minimization, as age group is already one of the prognostic factors included in the minimization algorithm.

Additionally, in case there are participants who sign the ICF and are randomized but do *not* receive the study intervention; additional patients will be enrolled in order to achieve the planned sample size. Also in the case of participants who sign the ICF, are randomized, receive the study intervention, and subsequently withdraw, or are withdrawn or discontinued from the study prior to completion of Day 90 assessments, or who do not have any efficacy assessments after Day 90, extra participants will be enrolled to achieve the planned sample size.

When enrolling additional participants, the participants who either did not receive study intervention, withdrew prior to the Day 90 assessments, or who do not have any efficacy assessments after Day 90 will *not* be included in the imbalance calculations used to implement the minimization algorithm, since these participants do not contribute to the primary analysis. In this way, participants enrolled additionally will be assigned to treatments to minimize imbalance across all participants expected to have data for the final analysis.

